 5. The FX-635™ Laser is activated
 6. The laser diodes laze each of these 3 areas for 15 minutes simultaneously.
 7. The procedures listed in 4. through 6. above is repeated for the left foot.
 8. The investigator and the subject remove the safety glasses.
 9. The subject rises and leaves the procedure administration room.

At each of the procedure administration test site visits, the investigator performs an adverse events evaluation.

PROCEDURE ADMINISTRATION PHASE MEASURES

DAILY MEASURES

Commencing on the same day as the first study procedure administration with the Erchonia® FX-635™ is administered, the subject will begin to record the required information in the Subject Daily Diary, as applicable, at home.

FOLLOWING EACH PROCEDURE ADMINISTRATION

Within 10 minutes following administration of each of the first 11 study procedure administrations with the Erchonia® FX-635™, the subject will record the following at the test site:

- Visual Analog Scale (VAS) Degree of Foot Pain Rating
- Adverse Events Evaluation

POST-PROCEDURE ACTIVITIES

POST-PROCEDURE EVALUATION PHASE

The post-procedure administration evaluation phase of this study will commence immediately following completion of the procedure administration phase and will last 3 months (about 12 weeks).

POST-PROCEDURE EVALUATION VISITS AND MEASURES

There will be 4 post-procedure evaluation visits. The first post-procedure evaluation visit will occur at the test site, and the remaining three post-procedure evaluation visits will take place at the subject's home. The subject will be provided with pre-dated case report forms on which to record the required information on each of those three post-procedure days, and a staff member at the investigator's test site will contact the individual on the designated day to remind him or her to record the required information. These visits, and the associated measures to be recorded at each visit, as listed and described, and according to the methodology outlined, in the STUDY TEST BATTERY section above are as follows:

DAILY MEASURES: AT HOME

The subject will continue to record the required information in the Subject Daily Diary, as applicable, at home, through to the 4 weeks post-procedure evaluation visit.

STUDY ENDPOINT EVALUATION: FOLLOWING COMPLETION OF THE PROCEDURE ADMINISTRATION PHASE: AT THE TEST SITE

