6. K041139; 09/30/04: "The Erchonia EML Laser is indicated as an adjunct to liposuction procedures of the thighs, hips and stomach for reduction of pain associated with the recovery process."

Evaluation Time Point

The study end evaluation time point at which primary study success will be analyzed is at six weeks post-baseline, following completion of the 12th and final study procedure administration with the Erchonia® FX-635™.

Null Hypothesis: There will be no statistically significant difference in the proportion of individual successes, as defined, between the test and control groups.

Alternative Hypothesis: There will be a statistically significant difference in the proportion of individual successes, as defined, between the test and control groups, to the effect of 35% or greater.

SECONDARY EFFICACY OUTCOME MEASURES

Secondary efficacy outcome measures will be evaluated for the following four data sets:

1. The blinded data set only attained from subjects who were initially enrolled in either the test or placebo procedure group and will not include active procedure test data attained from placebo subjects who partook in the post-study open-label procedure administration period after blinding was broken.

For this group, the following secondary efficacy outcome measure will be evaluated:

- a) Change in VAS rating across and between all study evaluation time points within and between treatment groups
 - b) Change in scores on the Neuropathic Pain Symptom Inventory (NPSI) across and between all evaluation points within and between treatment groups
 - c) Differences in the use of rescue pain medication between procedure groups across study duration
2. The combined data set comprising the blinded data set attained from subjects who were initially enrolled in either the test or placebo procedure group, and the active procedure test data attained from placebo subjects who partook in the post-study open-label procedure administration period after blinding was broken, comparing combined test (blinded and non-blinded) to placebo data

For this group, the following secondary efficacy outcome measure will be evaluated:

- a) Change in VAS rating across and between all study evaluation time points to study endpoint evaluation within and between treatment groups
- b) Changes in scores on the Neuropathic Pain Symptom Inventory (NPSI) across and between all evaluation points to study endpoint evaluation within and between treatment groups

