For this group, the following secondary efficacy outcome measure will be evaluated:

- d) Change in VAS rating across and between all study evaluation time points to study endpoint evaluation within and between treatment groups

- e) Changes in scores on the Neuropathic Pain Symptom Inventory (NPSI) across and between all evaluation points to study endpoint evaluation within and between treatment groups
- f) Differences in the use of rescue pain medication between procedure groups across study duration to study endpoint evaluation.

STATISTICAL METHODS

Efficacy analysis will be according to the intent to treat (ITT) principle by last observation carried forward (LOCF).

Intent to Treat: Subjects will be included in the analysis if they were randomized to study procedure group, had a valid baseline visit including the required Low Back Pain VAS recordings; and received the first study procedure administration.

Last observation carried forward: Missing data will be handled by carrying forward the last observation.

Per-protocol analysis will also be performed for the set of all subjects who were randomized to procedure group and completed the study according to the full protocol.

STATISTICAL ANALYSIS

The primary analysis of efficacy will be through the application of:

- 1) **Fisher's exact test** to compare the proportion of success between the test and the control groups, considering that randomization has been diligently conducted and important covariates between the two groups are well balanced.
- 2) **Parametric ANCOVA model** analysis with the mean change from baseline to study endpoint in foot pain ratings on the VAS as the dependent variable, procedure group as the independent variable of interest and baseline average foot pain VAS rating as a covariate. A two-tailed significance level of 5% will be considered to be statistically significant.

Covariates: The following potential covariate baseline variables will be adjusted, as applicable, through application of an ANCOVA analysis for the continuous variables and linear regression analysis for categorical variables.

- ✓ Baseline VAS rating
- ✓ Baseline NPSI total score
- ✓ Duration of foot pain
- ✓ Time since Diabetes diagnosis
- ✓ Insulin dependent versus non-insulin dependent Diabetes
- ✓ Age
- ✓ Gender

Secondary Measures Analysis

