- The secondary measures that are continuous variables will be analyzed through parametric analysis using ANCOVA. A two-way significance level of 5% will be considered to be statistically significant.
- The secondary measures that are categorical will be evaluated through linear regression analysis.

Satisfaction with Study Outcome Ratings: will be tabulated according to category and reported as percentages. Satisfaction levels will be correlated with subject individual study success and recorded changes in foot pain VAS ratings from Baseline to post-procedure evaluations.

BLINDING EFFICACY EVALUATION

Statistical evaluation of blinding efficacy will be performed as follows:

- (i) The percentage of subjects who correctly perceived their procedure group allocation and the percentage of subjects who did not correctly perceive their procedure group allocation will be calculated.
- (ii) The percentage of times the assessment investigator correctly perceived subjects' procedure group allocation and the percentage of times the assessment investigator did not correctly perceive subjects' procedure group allocation will be calculated.
- (iii) The Fischer's Exact categorical analysis technique for comparison of proportion of successes (accurate procedure group allocation determination) between actual active and placebo subject groups will be performed.

It is anticipated that the results of the Fischer's Exact analysis will not be statistically significant; that is, it is anticipated that both subjects assigned to the active procedure group and subjects assigned to the placebo procedure group will demonstrate a high percentage of accuracy of group allocation determination if the study treatment proves efficacious. Similarly, it is anticipated that assessment investigators will demonstrate a high percentage of accuracy of group allocation determination for both subjects assigned to the active procedure group and subjects assigned to the placebo procedure group, if the study treatment proves efficacious. Therefore, it should be noted that lack of a statistically significant Fischer's Exact analysis result will be considered an indicator of study blinding efficacy, providing additional support to study outcome efficacy, particularly if appropriately supported by the reasoning statements, as explained below.

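### The plan compares repeated VAS and NPSI scores across and between time points but names only ANCOVA, which cannot compare visits if run per visit and gives wrong standard errors if visits are pooled

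*Combined protocol and SAP*

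**What the plan says.** Under Secondary Efficacy Outcome Measures, data set 1 (blinded data only) lists "Change in VAS rating across and between all study evaluation time points within and between treatment groups" and "Change in scores on the Neuropathic Pain Symptom Inventory (NPSI) across and between all evaluation points within and between treatment groups". The later data sets repeat these outcomes up to the study endpoint.

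The method is in Secondary Measures Analysis: "The secondary measures that are continuous variables will be analyzed through parametric analysis using ANCOVA". It continues: "A two-way significance level of 5% will be considered to be statistically significant". The section does not say whether the model is fitted once per visit or once to all visits together.

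The only ANCOVA written out is in the Statistical Analysis subsection, for the primary evaluation. It takes change from baseline to endpoint as the outcome, with "procedure group as the independent variable of interest and baseline average foot pain VAS rating as a covariate". That is one row per subject.

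The ratings come from two phases. VAS is recorded on treatment "Within 10 minutes following administration of each of the first 11 study procedure administrations". Afterwards, "There will be 4 post-procedure evaluation visits": VAS is taken at all four (endpoint, two weeks, four weeks, three months) and NPSI at three (endpoint, four weeks, three months). Statistical Methods fills missing data by last observation carried forward.

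**The concern.** ANCOVA in its ordinary form assumes one independent value per subject. The stated outcomes ask for more, namely comparisons between visits and within groups, on ratings that come repeatedly from the same 64 people. Nothing in the plan tells the analyst how to handle that dependence.

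Two readings are open, and neither delivers what the outcome list asks for. Fitted visit by visit, the method leaves time-point comparisons without an analysis. Fitted to stacked visits, it treats correlated ratings as independent. The plan does not choose between them, so the choice could be made after the data are seen.

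The time course on treatment and the persistence of any effect to three months depend on these comparisons, and the study is intended to support a 510(k) submission.

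**Working it through.** **The plan's own figure.** The documents give no figure for the repeated-measures comparisons. The sample size does reproduce. With 55% v 20%, two-sided 5%, 80% power and pooled proportion 0.375, n = [1.96·√(2·0.375·0.625) + 0.8416·√(0.55·0.45 + 0.20·0.80)]² / 0.35² = (1.3419 + 0.5372)² / 0.1225 = 28.8, so 29 per group. It rests on the responder endpoint and does not depend on this point.

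**Inputs from the documents.** 32 subjects per arm; VAS ratings after baseline 11 + 4 = 15, of which 4 are post-procedure evaluations; NPSI scores after baseline 3.

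**Assumption.** The within-subject correlation is not given. I take a raw correlation ρ of 0.3, 0.5 and 0.7, equal between all pairs of ratings, baseline included.

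**Step 1: correlation left after baseline adjustment.** With unit variance, two later ratings have covariance ρ − ρ² given baseline, and each has variance 1 − ρ². So r = (ρ − ρ²)/(1 − ρ²) = ρ/(1 + ρ), which is 0.231, 0.333 and 0.412.

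**Step 2: one ANCOVA per visit.** There is one row per subject, so the standard error is correct. In 4,000 simulated null trials per setting, the between-arm type I error was 0.042 to 0.059, nominal within simulation error. The model contains one visit only, so it gives no visit-to-visit contrast.

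**Step 3: one ANCOVA on all rows, between arms.** With m ratings per subject, true SE / reported SE = √(1 + (m − 1)r), and type I error ≈ 2[1 − Φ(1.96/ratio)]. Example, m = 4 and ρ = 0.5: √(1 + 3·0.333) = 1.41; 1.96/1.41 = 1.39; type I error 0.166.

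| Ratings pooled | SE ratio, ρ = 0.3 / 0.5 / 0.7 | Type I error |
|---|---|---|
| NPSI, m = 3 | 1.21 / 1.29 / 1.35 | 10.5% / 12.9% / 14.7% |
| VAS evaluations, m = 4 | 1.30 / 1.41 / 1.50 | 13.2% / 16.6% / 19.0% |
| All VAS, m = 15 | 2.06 / 2.38 / 2.60 | 34.1% / 41.0% / 45.1% |

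Simulations agree within about two percentage points: 10–15% for NPSI, from 13–19% to 14–20% for the four VAS evaluations, and from 34–43% to 35–45% for all 15 ratings.

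**Step 4: the same pooled model, visit against visit.** Reported SE / true SE = 1/√(1 − r) = 1.14, 1.22 and 1.30. The type I error falls to about 2.5%, 1.6% and 1.1%, so these tests are conservative and lose power.

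**Step 5: check that accounting for the repeats cures it.** ANCOVA on each subject's mean change, one row per subject, gave type I error of 0.046 to 0.054 in all settings.

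**The case against.** The strongest reply is that the plan never says visits are stacked. Its one explicit ANCOVA has one row per subject. Applied at each visit in data set 1, that model gives valid between-arm tests, including those for persistence at two weeks, four weeks and three months. This stands. A reader might infer that the standard errors for all the repeated-score comparisons are wrong; the documents do not support that.

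Three other strong readings also fail.

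- An arm-by-time interaction is not named as an outcome. The text asks for comparisons across and between time points and groups.
- The repeated VAS ratings are not the only evidence beyond the endpoint rating. Endpoint NPSI, rescue medication use and satisfaction are also collected.
- Putting ρ = 0.3 to 0.7 straight into 1 + 14ρ gives SE ratios of √5.2 = 2.28 to √10.8 = 3.29, hence type I error of about 39–55%, and time-contrast factors 1/√(1 − ρ) of 1.2 to 1.8. That requires ρ to be the correlation remaining after baseline adjustment, or baseline to be unrelated to later ratings. With a raw correlation shared with baseline, the figures in the working apply.

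It can also be said that the 11 session ratings belong to the procedure administration phase and may not count as study evaluation time points. That is a fair reading, and it makes the 3- and 4-rating rows the more relevant ones. They still exceed 5% throughout.

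A mixed model is not the only valid remedy: per-visit ANCOVA plus within-subject change scores would also serve. The plan specifies neither. Under the per-visit reading that the reply relies on, comparisons between visits still have no stated method.

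**Conclusion.** The point holds as a gap between the stated secondary outcomes and the stated method. Per-visit ANCOVA is sound between randomised arms in data set 1 but leaves comparisons between time points without an analysis. Pooled ANCOVA without a subject term would give a between-arm type I error of about 10–15% (NPSI), 13–20% (four VAS evaluations) or 34–45% (all 15 VAS ratings), and time-contrast standard errors too large by about 1.1 to 1.3.

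These sizes rest on an assumed equal raw correlation of 0.3 to 0.7 shared with baseline, complete data and 32 per arm. They describe what pooling would do; the documents do not show that pooling is intended. The primary Fisher test, the endpoint ANCOVA and the sample size are untouched. The change should be made before analysis, but it concerns secondary results only.

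**What to change.** For data set 1, replace ANCOVA for VAS and NPSI over time with a mixed model for repeated measures.

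- **Fixed effects:** arm, visit, arm-by-visit and baseline score.
- **Within-subject errors:** correlated, with the structure fixed in advance. Unstructured is feasible: 4·5/2 = 10 parameters for the four VAS evaluations and 3·4/2 = 6 for the three NPSI visits. Kenward-Roger degrees of freedom would suit this sample size.
- **Data:** observed values, not values filled by last observation carried forward.
- **Reporting:** read arm differences at each visit and visit-to-visit changes from the model's contrasts.
- **Session ratings:** model the 11 on-treatment VAS ratings separately, for example with a random intercept and slope per subject. An unstructured matrix there would need 11·12/2 = 66 parameters from 64 subjects.

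This covers data set 1 only. Data set 2, described as "comparing combined test (blinded and non-blinded) to placebo data", can place the same placebo subjects on both sides, and data set 4 compares their placebo phase with their open-label phase. Those analyses need same-subject data to be paired even at a single time point.

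The cost is SAP wording, standard software, a little more analysis work and a covariance choice made in advance. No new data or subjects are needed.

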The primary efficacy outcome evaluation will be performed on the blinded data attained from subjects who were initially enrolled in either the test or placebo procedure group and will not include active procedure test data attained from placebo subjects who partook in the post-study open-label procedure administration period after blinding was broken.

Subjects meeting Individual Success Criteria

The individual subject success criteria defined as a 30% or greater decrease in self-reported VAS pain rating at study endpoint relative to baseline.

Overall Study Success Criteria

Overall study success criteria defined as at least a 35% difference between procedure groups, comparing the proportion of individual successes in each group. It is anticipated that about 55% of subjects in the test group will meet the individual success criteria and about 20% of subjects in the control group will meet the individual success criteria.

The clinical relevance of a 30% change in VAS score has been well previously established by FDA's Division of Surgical, Orthopedic and Restorative Devices through numerous pre-IDE reviews, the results of said studies that were subsequently used to successfully support various pain-reduction related indications for various Erchonia Corporation light therapy devices under Product Code NHN for the 510(k)s listed below over the past 8 years:

1. K180197: *Erchonia*® FX-635: is indicated for the following two indications:
 - a. as an adjunct to provide relief of minor chronic low back pain of musculoskeletal origin.
 - b. as an adjunct to reducing chronic heel pain arising from plantar fasciitis.
2. K101430; 06/22/10: "The MLS-AC DermaScanner™ is indicated, while using the red diodes, for adjunctive use in providing temporary relief of minor chronic neck and shoulder pain of musculoskeletal origin."
3. K100509; 06/08/10: "The Erchonia THL1 is indicated for use in providing temporary relief of minor chronic neck and shoulder pain of musculoskeletal origin."
4. K072206; 04/24/08: "The Erchonia EML Laser is indicated for the temporary reduction in post -surgery pain at 24 hours after surgery following breast augmentation surgery."

5. K050672; 06/02/05: "The Erchonia EVRL Laser is generally indicated while using the red diode for adjunctive use in providing temporary relief of minor chronic neck and shoulder pain of musculoskeletal origin."

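### Secondary outcomes are tested within and between arms at every time point at an unadjusted 5%, so a before-after fall in the laser arm or one isolated time point can be reported as significant without showing a device effect

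*Combined protocol and SAP*

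**What the plan says.** Under Secondary Efficacy Outcome Measures, the first (blinded) data set has three items:

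- VAS: "Change in VAS rating across and between all study evaluation time points within and between treatment groups".
- NPSI: "Change in scores on the Neuropathic Pain Symptom Inventory (NPSI) across and between all evaluation points within and between treatment groups".
- Rescue medication: "Differences in the use of rescue pain medication between procedure groups across study duration".

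Secondary Measures Analysis assigns continuous secondary measures to ANCOVA and adds: "A two-way significance level of 5% will be considered to be statistically significant". Categorical secondary measures go to linear regression, with no level stated.

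The visit schedule fixes the number of looks. During treatment, VAS is recorded "Within 10 minutes following administration of each of the first 11 study procedure administrations". After treatment, "There will be 4 post-procedure evaluation visits": study endpoint, 2 weeks, 4 weeks and 3 months, each with a VAS rating. NPSI is repeated at three of the four (not at 2 weeks).

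The same measures are then repeated, up to study endpoint, in further data sets that bring in open-label data from placebo subjects. The text says "Secondary efficacy outcome measures will be evaluated for the following four data sets" but lists five, the fifth repeating the third. A per-protocol analysis and site-by-site analyses are also planned.

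Nowhere does the plan name a key secondary outcome, set a testing order, adjust alpha, or say that secondary or within-arm results are descriptive.

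**The concern.** There are two separate problems.

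First, a within-arm change is an uncontrolled before-after comparison. Subjects enter with a two-day average VAS of at least 50, so some regression to the mean is plausible. Rescue medication is allowed throughout. The plan also anticipates that "about 20% of subjects in the control group will meet the individual success criteria". Any improvement shared by both arms can give a small p-value in the laser arm, and only the between-arm comparison is protected by randomisation.

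Second, even the between-arm comparisons are numerous, and each is judged at 5%. One significant time point among many is weak evidence when nobody said beforehand which one mattered.

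The results are intended to support a 510(k) submission. A trial that misses its primary responder comparison could still list significant secondary pain reductions, and the plan gives a reader no basis for discounting them.

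**Working it through.** **The plan's own figures.** The plan states no family-wise error rate for the secondary outcomes, so there is none to reproduce. Its sample size confirms the inputs used here. For 55% against 20%, two-sided 5%, power 80%:

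n = [1.96·√(2·0.375·0.625) + 0.842·√(0.55·0.45 + 0.20·0.80)]² / 0.35² = 28.8, so 29 per group. The plan inflates this to 32.

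**Counting the comparisons (blinded data set, between arms).**

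- VAS: 11 session ratings + 4 post-procedure ratings = 15, or 4 if only the post-procedure visits count as evaluation time points.
- NPSI total: 3 post-baseline visits.
- Rescue use: taken as 1.
- Broad total: 15 + 3 + 1 = 19.

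The endpoint VAS comparison also appears as an ANCOVA under the primary analysis. It is kept in the count, and dropping it would lower the figures slightly.

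**Within-arm test.** The plan names no method, so I assume a paired t-test on percent reduction in VAS, 32 laser subjects, a normal distribution, and a laser no better than placebo. Both arms then have 20% of subjects at or above a 30% reduction. This fixes the mean: mean = 30 − 0.8416·SD. The noncentrality is mean/(SD/√32), and the critical value is 2.04 on 31 df.

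| Assumed SD (points) | Implied mean reduction | Noncentrality | P(significant, two-sided) |
|---|---|---|---|
| 20 | 13.2 | 3.72 | 95% |
| 25 | 9.0 | 2.03 | 50% |
| 30 | 4.8 | 0.90 | 14% |
| 35 | 0.5 | 0.09 | about 5% (3% for a fall) |

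At SD 36 the implied mean is 30 − 0.8416·36 = −0.3, a slight worsening. The result therefore depends heavily on an SD that the documents do not give.

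**Between-arm tests.** With no true difference and k equally correlated normal test statistics (correlation ρ), the chance of at least one significant result is

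1 − ∫ φ(u)·[Φ((1.96 − √ρ·u)/√(1−ρ)) − Φ((−1.96 − √ρ·u)/√(1−ρ))]^k du.

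Dropping the second Φ term counts only results favouring the laser.

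| Comparisons | ρ = 0.3 | ρ = 0.5 | ρ = 0.7 |
|---|---|---|---|
| 15 VAS, either direction | 46% | 36% | 26% |
| 15 VAS, favouring laser | 23% | 18% | 13% |
| 4 VAS, either direction | 17% | 16% | 13% |
| 4 VAS, favouring laser | 9% | 8% | 6.5% |
| 19 (VAS, NPSI, rescue), either direction | 53% | 41% | 28% |

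The nominal reference is 5% in either direction, or 2.5% in the laser's favour. The further data sets, the per-protocol repeat and the site analyses are not counted.

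**The case against.** The strongest reply is that study success is defined once: a 35-point difference in responders at six weeks, in the blinded data. No secondary result can establish or overturn it. That stands. A reader might infer that a significant secondary result counts as a positive trial, but nothing in the plan says so. The risk lies in what is reported and promoted.

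A reader might also infer that significant pain relief is likely to be reported even if the laser is no better than placebo. The documents do not support that. The within-arm probability runs from 95% down to about 5% over plausible SDs, and the documents give neither an SD nor a mean change. Nor does a 20% placebo responder rate imply an average fall, since it is compatible with a mean change of zero. Between-arm results favouring the laser reach 13% to 23% over 15 looks. That is inflated, but not likely.

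The 5% sentence sits in a bullet on ANCOVA, and the only ANCOVA specified compares groups. Reading it as an explicit 5% rule for within-arm tests goes further than the text. What can be said is that within-arm change is a listed outcome, its test is undefined, and nothing marks it as descriptive.

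Finally, the count of 15 is the broad reading. The protocol uses evaluation visit for the four post-procedure visits and lists the session ratings separately. On four looks the inflation is modest. The plan does not say which reading applies, which is itself a reason to specify it.

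**Conclusion.** The point holds as a gap in specification and error control for the secondary outcomes. The plan promises within-arm and between-arm comparisons at all time points and applies an unadjusted 5% level to continuous measures. It provides no hierarchy and no descriptive label.

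The within-arm comparison is the more serious part, because its p-value does not address whether the device works, whatever the number of looks. Its chance of being significant with no device effect is 95%, 50%, 14% or about 5% at an SD of 20, 25, 30 or 35 points. This rests on a paired t-test, normality and 20% responders in both arms. For between-arm VAS results in the laser's favour, the error rate rises from 2.5% to 13–23% over 15 looks, or 6.5–9% over four, at assumed correlations of 0.3 to 0.7.

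The primary conclusion is unaffected. The plan should be changed because the results are meant for a regulatory submission and the remedy is simple.

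**What to change.** In Secondary Efficacy Outcome Measures and Secondary Measures Analysis:

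1. Report within-arm changes as means with 95% confidence intervals and no p-values.
2. Name one between-arm key secondary outcome in the blinded data set. The choice is the sponsor's; VAS change at 4 weeks post-procedure is one example. Test it at two-sided 5% only if the primary responder comparison (Fisher's exact test) is significant.
3. Label all other secondary comparisons as supportive and report them as between-arm estimates with 95% confidence intervals.
4. State whether the 11 session ratings count as evaluation time points.

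This changes wording only, with no added subjects, visits or data. The cost is that fewer results can be called significant.
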